6.9 ANALYSIS SOFTWARE

Data manipulation and generation of listings and tables for all safety data and disposition and participation data will be performed using SAS Enterprise Guide Software version 7.12.

6.10 DATA CHECKING, MANAGEMENT AND SECURITY

Quality control review of listings and tables will be undertaken to ensure data contained in these documents correctly represent data recorded in the study databases. Where review by the Sponsor identifies erroneous values or the requirement for modification, the appropriate SAS program will be updated, and the document recreated. Updated documents will undergo a repeat of the quality control process. Where modification to electronic data files is required (e.g., SAS program, analysis data file), the old file will be retained.

	STATISTICAL ANALYSIS PLAN	QP17C19
		Page 26 of 53

All electronic data storage systems containing study data or analysis information will be password protected at all times, with access restricted to authorised CNS staff. Multisite backup of all electronic data and files will be performed daily.

6.11 ARCHIVING

All statistical analysis documents and records are to be retained for a minimum of fifteen years after trial completion. Written agreement from the Sponsor must precede destruction of the same.

	
STATISTICAL ANALYSIS PLAN
	
QP17C19

		
Page 27 of 53

SECTION 7: STATISTICAL METHODOLOGY FOR PHARMACOKINETIC DATA

7.1 GENERAL CONSIDERATIONS

Listings of pharmacokinetic data will be generated by CNS. Summary statistics, non-compartmental analysis (NCA), and graphical representation of PK data and their statistics will be performed by IntiQuan.

NCA of PK data will be performed to determine the AUC_{0-168h} , AUC_{last} , AUC_{0-inf} , C_{max} , t_{max} , $t_{1/2}$, t_{lag} , CL/F , V_z/F and λ_{inf} for OZ439 and PQP for the subjects in QP17C19.

7.2 SOURCE OF DATA

Plasma concentration of OZ439 and PQP, treatment and blood sampling information will be recorded and merged to produce source PK concentration data for analysis.

7.3 DATA HANDLING

Data Imputation for Pharmacokinetic Concentration Data Reporting

No imputations will be done for missing concentration values or missing time information, i.e., records with missing concentrations or times will be discarded. Concentrations that are below the lower limit of quantification (LLOQ) are defined as being below limit of quantification (BLQ) and will be reported as "BLQ" in data listings. For calculation of geometric means, geometric standard deviation (SD) and geometric coefficient of variation (CV%) concentration values reported as BLQ will be set to $\frac{1}{2} \times LLOQ$ and for all other summary statistics concentration values reported as BLQ will be set to zero.

Data used for Pharmacokinetic Estimation

In general, only concentration values above the LLOQ are used, hence, BLQ values are discarded with the following exceptions:

- Individual BLQ concentration values between the first dosing time and the first time point above LLOQ (i.e. during lag-time) are set to 0 and included in the PK evaluation.
- Pharmacokinetically plausible concentration value(s) below LLOQ at time points between two measurable concentration values are replaced by the LLOQ/2 value, flagged and included in the PK evaluation.

Actual time from dose administration will be used for parameter estimation except for the pre-(first) dose data point which will be set to the nominal time of 0 hour. Data with missing time information will be discarded.

7.4 METHODS

Data Listings

Individual data listings containing the drug concentrations of OZ439 and PQP will be represented with same number of decimal places or significant digits as the source data.

Calculation of descriptive statistics

The CV% is calculated as

$$CV\% = 100 \cdot \frac{SD}{mean}$$

The geometric SD is calculated as

$$SD_{geometric} = e^{SD(\ln(datavalues))}$$

The geometric CV% is calculated as

$$CV\%_{geometric} = 100 \cdot \sqrt{e^{SD(\ln(datavalues))^2} - 1}$$

Summary Tables

The concentration time courses will be represented in tables stratified by dose group. Descriptive statistics will be reported for each scheduled time-point with the precision as given in Table 7.

Table 7. Number of decimal places for PK concentration summary statistics

Descriptive statistic	Number of decimal places
Number of subjects	none
Geometric mean	i + 1
Median	i + 1
Minimum	i
Maximum	i
Arithmetic mean	i + 1
SD	i + 1
CV%	1
i = number of decimal places in source	

Figures

The concentration-time courses will be represented graphically based on following plots.

1. Individual profiles (one panel per subject) with concentrations of OZ439 and PQP on linear scale
2. Individual profiles (one panel per subject) with concentrations of OZ439 and PQP on log₁₀ scale
3. Spaghetti plots of individual profiles stratified by dose group with concentrations on linear scale, separately for OZ439 and PQP.
4. Spaghetti plots of individual profiles stratified by dose group with concentrations on log₁₀ scale, separately for OZ439 and PQP.
5. Summary plots of arithmetic means per scheduled timepoint presenting all dose groups in one panel, separately for OZ439 and PQP. Subjects are summarized per

	STATISTICAL ANALYSIS PLAN	QP17C19
		Page 29 of 53

dose group. Plots on both linear and on log₁₀ scale for the concentrations will be produced. Error bars representing +/- 1 arithmetic SD will be included.

6. Summary plots of geometric means per scheduled timepoint presenting all dose groups in one panel, separately for OZ439 and PQP. Plots on both linear and on log₁₀ scale for the concentrations will be produced. Error bars representing +/- 1 geometric SD will be included. If the (geometric mean – geometric SD) value is zero or negative, then only the value for (geometric mean + geometric SD) will be displayed as error bars on the plot.

Pharmacokinetic Parameter Estimation (NCA)

Definition and calculation of Pharmacokinetic Parameters

Table 8 provides a list of definitions for PK parameters that will be calculated in this study.

Table 8. Definitions and calculation of PK Parameters

Parameter	Description
AUC _{last}	Area under the plasma concentration-time curve, calculated using linear-up logarithmic down trapezoidal summation from time zero to the last measurable concentration.
AUC _{0-inf}	Area under the plasma concentration-time curve from time zero to infinity, AUC _{0-inf} is calculated as the sum of AUC _{last} plus the last measurable plasma concentration divided by elimination rate constant [λ_{inf}].
C _{max}	Maximum observed drug concentration in observed individual concentration time profile.
t _{max}	Time to maximum observed drug concentration within a dose interval. If the maximum value occurs at more than one time point, t _{max} is defined as the first time point with this value.
t _{1/2}	Apparent elimination half-life, calculated as $\ln[2]/\lambda_{inf}$.
t _{lag}	Elapsed time from dosing at which drug concentration was first quantifiable.
CL/F	Apparent total body clearance after extravascular administration, calculated as Dose/AUC _{0-inf} .
V _Z /F	Apparent total volume of distribution at the terminal phase after extravascular administration, calculated as Dose/ $[\lambda_{inf} \times \text{AUC}_{0-inf}]$.
λ_{inf}	Apparent terminal elimination rate constant, calculated by linear regression of the terminal linear portion of the log concentration vs. time curve. The terminal slope is calculated using the Best slope algorithm that sequentially fits $(\log(y) \sim x)$ from the last point of x to the previous points with at least 3 points. It chooses a slope with the highest adjusted R-square. If the difference is less than 1e-4, it picks a longer slope. x here represents the times of PK samples and y their observed concentrations.

	STATISTICAL ANALYSIS PLAN	QP17C19
		Page 30 of 53

Tabular and graphical presentation of NCA results

Values for λ_{inf} , $t_{1/2}$, CL/F and Vz/F, AUC_{0-inf} for a subject will only be reported if the following criteria for the log-linear phase for the concentration-time data are met:

- A minimum of 3 measurable concentration-timepoints during the log-linear portion of the terminal elimination phase, excluding C_{max}.
- $r^2 > 0.80$ for the regression of the log-concentration time data during the terminal elimination phase.
- Negative slope for log regression fit.
- Extrapolated portion of AUC_{0-inf} < 20% of total AUC_{0-inf}.

Individual PK parameters will be reported as a table grouped by dose level with stratification for dose of the second treatment and overall. Individual and dose-normalized PK parameters (C_{max} and AUCs) will be visualized by dose level for PQP and OZ493, separately.

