To achieve eradication of malaria, long-lasting, single-dose treatments that completely clear malaria parasites from the body and provide a period of protection following the treatment are required. These ideal types of medicines are referred to as single encounter radical cures (SERC). The WHO and Medicines for Malaria Venture (MMV) have identified the key properties that a SERC must have. These properties are defined by Burroughs et al. (2017) in the antimalarial target product profile (TPP) [5]. A key requirement of a target product is the inclusion of two or more active molecules with different mechanisms of action. The aim of including two or more active compounds is to achieve an increased barrier to resistance by using drugs with different mechanisms of action, forcing the parasite to develop multiple simultaneous mutations in order to become resistant. Furthermore, in a combination therapy, one of the two active compounds should have a rapid onset of action, killing most of the parasite. Both active compounds should maintain plasma concentrations above the minimal parasitocidal concentration (MPC) approximately the same time and ensure complete elimination of all parasites.

Artefenomel (OZ439) is a novel trioxolane and a front-runner candidate for inclusion in a new antimalarial combination. It is a synthetic ozonide with potency comparable to artemisinin, with a rapid parasite clearance rate of approximately 3.6 h for *P. falciparum*. Additionally, OZ439 has a substantially longer half-life than artemisinin (46 - 62 h as opposed to 3 h for artemisinin [6]). For these reasons, clinical studies in which artefenomel is combined with a companion drug with a different mechanism of action are being planned or are currently in progress.

Piperaquine is a bis-4-aminoquinoline and was used mainly in China from the 1960's to the 1980's as an antimalarial monotherapy. In the 1980's, it became clear that parasite resistance had developed to PQP monotherapy. PQP is characterised by slow absorption and a long elimination half-life (4-5 weeks) and is now widely used in combination with dihydroartemisinin as a fixed dose ACT. The successful pairing of PQP with an artemisinin, together with its long biological half-life, means PQP is potentially a good drug partner for OZ439.

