### PK blood collection and processing

Blood sampling for PK analysis will be performed at scheduled time points immediately before dosing with OZ439 and PQP until 816 hours post dose (allowed time windows as described above)

Blood samples will be collected either by direct puncture or via an indwelling cannula inserted in a forearm vein. Details of the volume of blood collected are listed in Appendix 2.

A description of the required laboratory procedures will be described in the Laboratory Manual.

The actual sample collection date and time will be entered in the PK blood collection section of the eCRF. Any sampling problems will be documented in the eCRFs.

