### Prior to exit from the clinical unit

Subjects will be allowed to leave the clinical unit 72 hours post-OZ439 and PQP treatment at the Investigator's discretion.

The following procedures will occur prior to discharge from the clinical unit:

1. Perform symptom-directed physical examination at Investigator's discretion
2. Record vital signs.
3. Collect blood samples for haematology, biochemistry (including CRP biomarker), PK analysis and malaria 18S qPCR - 72 hours post-OZ439 and PQP dosing.
4. Obtain 12-lead ECG in triplicate
5. Record AEs and use of concomitant medications.

Out-patient monitoring post-OZ439 and PQP treatment (Day 12 up to Day 42±2)

Follow-up at either AM (approximately 08:00) or AM and PM (if necessary, approximately 12 hours apart) will be undertaken on an out-patient basis through visits post confinement for clinical evaluation and blood sampling.

The following procedures will take place during these visits:

1. Elicit information regarding any new medical conditions or illnesses.
2. Collect a blood sample for malaria 18S qPCR in the morning and in the evening on days 12 and 13 and then three times weekly or at Investigator's discretion based on parasitaemia until Day 42±2.
3. Collect blood samples for parasite lifecycle stage qPCR at the Investigator's discretion (Section 7.2.2).
4. Collect blood samples for PK analysis of OZ439 and PQP at 2, 96±48, 240±48, 336±48, 504±48, 672±48 and 840±48 hours after OZ439 and PQP administration.
5. Collect blood samples for haematology and biochemistry (including CRP biomarker) and urine for urinalysis at 336±48, 504±48 and 672±48 hours post-OZ439 and PQP administration or at the Investigator's discretion.
6. Collect optional blood samples for complement regulatory protein (if consented separately) at 96±2, 120±48, 168±48, 240±48 hours post-OZ439 and PQP.
7. Collect optional blood samples for immune cell characterisation (if consented separately) at 168±48 hours post-OZ439 and PQP.
8. Perform symptom-directed physical examination when signs or symptoms of malaria are identified and it is clinically indicated.
9. Record vital signs.
10. Record malaria clinical score if vital signs are abnormal or at Investigator's discretion.
11. Record AEs and use of concomitant medications.
12. Check subject diaries.

Rescue treatment with Riamet®

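### SAP 7.4 draws geometric error bars as mean plus or minus a ratio, which is wrong, and its 20% extrapolation limit may selectively withhold PQP half-life and clearance values

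*SAP*

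**What the plan says.** **Error bars.** SAP 7.4 (Calculation of descriptive statistics) defines geometric SD as exp(SD(ln(values))). For the geometric-mean concentration plots (item 6 under Figures, planned as Figure 14.2.1.2) it says: "Error bars representing +/- 1 geometric SD will be included". If the geometric mean minus the geometric SD is zero or negative, only the upper limit is kept: "geometric mean + geometric SD) will be displayed as error bars on the plot".

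**Extrapolation limit.** Under Tabular and graphical presentation of NCA results, SAP 7.4 says that λinf, t1/2, CL/F, Vz/F and AUC0-inf "for a subject will only be reported if the following criteria for the log-linear phase for the concentration-time data are met". There are four criteria: at least 3 terminal points, r² above 0.80, a negative slope, and an extrapolated part of AUC0-inf below 20%. The same rule serves both drugs. AUC0-168h, AUClast, Cmax, tmax and tlag are not subject to it.

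**PQP and sampling.** Protocol 2.1 states: "PQP is characterised by slow absorption and a long elimination half-life (4-5 weeks". Protocol 7.2.2 has PK samples taken "immediately before dosing with OZ439 and PQP until 816 hours post dose", while the out-patient schedule in Protocol 7.3.3 ends with "672±48 and 840±48 hours after OZ439 and PQP administration". Protocol 10.3.3 speaks of 28 days for the same parameters.

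**The concern.** A geometric SD multiplies and divides; it has no concentration unit. Adding it to a concentration gives a bar whose length depends on the unit chosen and says nothing about spread.

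The extrapolation limit raises two separate issues. By SAP Table 8, λinf is the terminal regression slope and t1/2 is ln 2/λinf. Neither uses the extrapolated area, and the other three criteria already test that regression. The limit also selects on the estimate itself: the tail is the last concentration divided by λinf, so a longer estimated half-life gives a larger tail and a greater chance of removal. For a drug sampled over about one half-life, the values that survive would tend to be the short half-lives and, correspondingly, the higher clearances. These are named secondary endpoints summarised in dose groups of 2 or 4, so one withheld value in a pair leaves n = 1.

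**Working it through.** The plan states no computed figure here to reproduce, only the 20% limit and the half-life.

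**1. Error bars.** Assumed example: geometric CV 50%.
- GSD = exp(√ln(1 + 0.5²)) = exp(0.472) = 1.60.
- GM 500: as written, 500 ± 1.60 = 498 to 502. Correct: 500/1.60 to 500 × 1.60 = 312 to 802.
- GM 0.05: as written, the lower limit is negative and dropped, and the upper is 0.05 + 1.60 = 1.65. Correct: 0.031 to 0.080.
- Unit dependence: 500 ng/mL is 0.5 µg/mL. In µg/mL the same data lose the lower bar and show an upper limit of 0.5 + 1.60 = 2.10, instead of 0.80. SAP section 7 fixes no unit for these plots.
- GSD is never below 1, so any GM at or below 1 always loses its lower bar. GM/GSD is always positive, so the zero-or-negative clause has a use only if literal subtraction is meant.

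**2. True extrapolated share for PQP.** Inputs: t1/2 28–35 days (Protocol 2.1) and last sample T = 34 days (816 h, Protocol 7.2.2). Let f be the share of AUC0-inf carried by the terminal phase. It is not in the documents, so it is an assumption.
- Share = f × 0.5^(T/t1/2).
- 0.5^(34/28) = 0.431 and 0.5^(34/35) = 0.510.
- At T = 35 days (840 h): 0.420 and 0.500.
- Across T = 28 to 37 days, which spans Protocol 10.3.3 and the late end of the 840 ± 48 h window: 0.40 to 0.57.
- At T = 34 days the share exceeds 20% when f is above 0.20/0.431 = 0.46 (28 days) or 0.20/0.510 = 0.39 (35 days).

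**3. The rule acts on the estimated slope.** SAP Table 8 takes the terminal slope with the highest adjusted R², using at least 3 points. That NCA was applied to simulated profiles at nominal times to 816 h. Assumptions: three exponentials, with faster half-lives of 72 h and 12 h sharing 1 − f equally; ka 0.3/h; 15% log-normal noise. Ranges are over terminal half-lives of 28 and 35 days.

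| f | Extrapolated share, no noise | Withheld, with noise |
|---|---|---|
| 0.4 | 14–16% | about 7% |
| 0.5 | 19–21% | 15–20% |
| 0.6 | 24–27% | 32–39% |
| 0.7 | 29–33% | 62–67% |
| 0.8 | 34–39% | 84–93% |

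These totals include profiles failing r² or slope. When the simulation was repeated with the reasons separated, the 20% limit alone removed about 5% at f = 0.4, 24–29% at 0.6 and 75–78% at 0.8.

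At f = 0.8 the median estimated half-life was 18–20 days among all profiles and 14 days among those reported, against a true 28–35 days.

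**4. OZ439.** With t1/2 of 46–62 h, 0.5^(816/62) = 0.0001 at most, so the limit does not bind.

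**The case against.** The best defence of the limit is that it is a prespecified reliability rule: it withholds doubtful values and miscalculates nothing. With about one half-life of sampling, PQP t1/2 is doubtful in any case. Exposure is still covered by AUClast and Cmax, clearance by the planned population PK model (SAP 9.4), and the primary PK/PD analysis uses concentrations, not NCA output. All of that stands and limits the consequence. It does not justify tying λinf and t1/2 to an area they do not use, and if every PQP half-life is doubtful, that argues for marking all of them rather than showing the shortest.

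A reader might go further and infer that every subject with a 4–5 week half-life must fail, or that the PQP summaries will be nearly empty. At f = 0.6, for example, the closed formula passes only half-lives below 34 × ln 2/ln(0.6/0.2) = 21.5 days; with an assumed median of 31.5 days and CV 30%, that is about 2 of 24 subjects. The documents do not support this. They do not give f, and the SAP applies the limit to the estimated slope, which tends to run short. Under that rule the simulation withheld 32–39% at f = 0.6, so most profiles passed.

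Nor should the short bias be put down mainly to the limit. At f = 0.8 the median across all profiles was already 18–20 days; the limit took it to 14.

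For the error bars, the only defence is loose wording, and the zero-or-negative clause rules that out.

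**Conclusion.** The error-bar rule is wrong as written and contradicts the SAP's own definition of geometric SD. Its reach is small: Figure 14.2.1.2, for both drugs, and no endpoint, test or table statistic.

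The extrapolation limit is a weakness that is cheap to remove, not a calculation error. It withholds λinf and t1/2 without need and favours short estimated half-lives. For PQP the effect could be anything from a few subjects (f about 0.4) to most (f about 0.8 or more). The documents do not allow a narrower statement, because f is not given and the withholding rates rest on the assumed profile shape and noise. The secondary PQP summaries may therefore be sparse and tilted short in groups of 2 or 4. OZ439 and the primary PK/PD model are not affected.

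**What to change.** 1. Draw geometric error bars from GM/GSD to GM × GSD and delete the zero-or-negative clause.
2. Apply only the points, r² and slope criteria to λinf and t1/2.
3. For subjects meeting those three criteria, list AUC0-inf, CL/F and Vz/F with the percent extrapolated, and flag values of 20% or more rather than withholding them.
4. For PQP, rely on AUClast for exposure and the population PK model for clearance; both are already planned.
5. State in the SAP and CSR that PQP t1/2 from about one half-life of sampling is probably underestimated, with or without the limit.

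The cost is SAP wording and small code changes; no new data are needed. The downside is that more uncertain PQP values will appear, which is why the flag and the statement in item 5 belong with the change.

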7.5 SOFTWARE AND WORKING DIRECTORY

All data processing, summary statistics, and NCA will be performed in R 3.5.1 using the IQRtools package 1.0.0 [IQR18].

7.6 REPORTING IN MAIN BODY OF CSR

The NCA results and key figures of the PK profiles will be reported in the main text of the CSR.

SECTION 8: STATISTICAL METHODOLOGY FOR PHARMACODYNAMIC DATA

8.1 GENERAL CONSIDERATIONS

Data listings and summary tables will be generated by CNS for the following,

- Parasitaemia data
- PD endpoints:
 - Parasite reduction ratio at 48 h (PRR₄₈) and parasite clearance half-life (PC_{t1/2})
 - Percentage of subjects with recrudescence of parasitaemia

Unless specifically mentioned otherwise, baseline is defined as the last observation prior to first treatment administration. If a baseline reading is missing, then an earlier measurement will be used.

	
STATISTICAL ANALYSIS PLAN
	
QP17C19

		
Page 31 of 53

8.2 SOURCES OF DATA

All parasitaemia data will be generated by the Queensland Paediatric Infectious Diseases (QPID) laboratory and transferred electronically to QIMR Berghofer, who will process the data and provide to CNS for the parasitaemia listing.

All PD data will be generated from processed parasitaemia data. Please refer to CTM QIMR SOP 87 for details regarding the processing of the parasitaemia data.

The contents of the Clinical Study Database and the processes that will be used for reconciliation and locking are described in more detail in the QP17C19 Data Management Plan.

8.3 DATA HANDLING

Handling of Replicates

The data will be recorded as triplicate parasitaemia values for each subject at each timepoint. These data will be summarised by calculating the arithmetic mean of the replicate \log_{10} parasitaemia to obtain the geometric mean per subject and timepoint.

Handling of Missing Data

For any replicates that were ND, the value was substituted with 1 prior to calculating the geometric mean. For calculation of the PRR_{48} and parasite clearance half-life, if all replicates within a timepoint for a participant were ND, the first timepoint with all ND was included in model fitting, and all other timepoints were set to missing. All regression analyses were performed using the mean \log_{10} parasitaemia. If no samples were all ND for a subject within 5 days post treatment, the last timepoint included was either 5 days post treatment or three timepoints after the minimum observed mean \log_{10} parasitemia.

